### 5.4.4.2. Treatment Delay

#### 5.4.4.2.1. *Criteria for Treatment Delay*

AGEN2034 administration should be delayed for the following:

- Any Grade  $\geq 2$  non-skin, drug-related AE with the following exceptions:
  - Do not delay treatment for Grade  $\geq 2$  Fatigue and laboratory abnormalities except for:
    - Delay dosing for Grade  $\geq 2$  serum creatinine (more than 1.5x baseline) toxicity
    - If a subject has a baseline AST, ALT, or total bilirubin that is within normal limits, delay dosing for drug-related Grade  $\geq 2$  toxicity;
- Any Grade  $\geq 3$  skin drug-related AE or suspected Stevens-Johnson syndrome (SJS) or toxic epidermal necrolysis (TEN)
- Any Grade  $\geq 3$  drug-related laboratory abnormality with the following exceptions for lymphopenia, AST, ALT, or total bilirubin:
  - Grade 3 lymphopenia does not require a dose delay.
  - If a subject has a baseline AST, ALT, or total bilirubin that is within normal limits, delay dosing for drug-related Grade  $\geq 2$  toxicity.
  - If a subject has baseline AST, ALT, or total bilirubin within the Grade 1 toxicity range, delay dosing for drug-related Grade  $\geq 3$  toxicity.
- Any AE, laboratory abnormality, or inter-current illness which, in the judgment of the investigator, warrants delaying the dose of study drug.

Subjects receiving AGEN2034 who have drug-related toxicities that meet the criteria for dose delay should have treatment delayed until retreatment criteria are met.

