**Table 7: Hepatic Immune-related Adverse Event Management Algorithm**

Hepatic Immune-related Adverse Events		
Grade of Liver Test Elevation (NCI CTCAE v4.03)	Management	Follow-Up
Grade 1 AST or ALT >ULN to 3 x ULN and/or total bilirubin >ULN to 1.5 x ULN.	
 
Continue AGEN2034 therapy per protocol.
 
	
 
Continue liver function tests (LFT) monitoring per protocol.
 
If worsens: treat as Grade 2 or Grade 3–4.
 

Grade 2 AST or ALT >3 to ≤5 x ULN and/or total bilirubin >1.5 to ≤3 x ULN.	
 
Delay AGEN2034 therapy per protocol.
 
Increase frequency of monitoring to every 3 days.
 
If subject has concurrent AST or ALT > 3 x ULN AND total bilirubin > 2 x ULN, Discontinue AGEN2034 therapy per protocol.
 
	
 
If returns to baseline: resume routine monitoring; resume AGEN2034 therapy per protocol.
 
If elevations persist >5 to 7 days or worsen: 0.5–1 mg/kg/day methylprednisolone IV or oral equivalent. When LFT returns to Grade 1 or baseline, taper corticosteroids over at least 1 month, consider prophylactic antibiotics for opportunistic infections, and resume AGEN2034 therapy per protocol.
 

Grade 3–4 AST or ALT >5 x ULN and/or total bilirubin >3 x ULN.	
 
Discontinue AGEN2034 therapy per protocol.
 
Increase frequency of monitoring to every 1–2 days.
 
1–2 mg/kg/day methylprednisolone IV or oral equivalent*.
 
Add prophylactic antibiotics for opportunistic infections.
 
Consult gastroenterology.
 
Consider obtaining MRI/CT scan of liver and liver biopsy if clinically warranted.
 
	
 
If returns to Grade 2: taper corticosteroids over at least 1 month.
 
If does not improve in > 3 to 5 days, worsens or rebounds: add mycophenolate mofetil 1 g twice daily. If no response within an additional 3–5 days, consider other immunosuppressants per local guidelines.
 

\*The recommended starting dose for Grade 4 hepatitis is 2 mg/kg/day methylprednisolone IV.

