**Table 8: Endocrine Immune-related Adverse Event Management Algorithm**

Endocrine Immune-related Adverse Events		
Endocrine Disorder	Management	Follow-Up
Asymptomatic thyroid-stimulating hormone (TSH) abnormality	
 
Continue AGEN2034 therapy per protocol.
 
If TSH < 0.5 x lower limit of normal (LLN) or TSH > 2 x ULN, or consistently out of range in 2 subsequent measurements: include free thyroxine (fT4) at subsequent cycles as clinically indicated; consider endocrinology consult.
 
	
Symptomatic endocrinopathy	
 
Evaluate endocrine function.
 
Consider pituitary scan.
 
Symptomatic with abnormal lab/pituitary scan: delay AGEN2034 therapy per protocol; 1-2 mg/kg/day methylprednisolone IV or oral equivalent; initiate appropriate hormone therapy.
 
No abnormal lab/ pituitary MRI scan but symptoms persist: repeat labs in 1-3 wk/MRI in 1 month.
 
	
 
If improves (with or without hormone replacement): taper corticosteroids over at least month and consider prophylactic antibiotics for opportunistic infections.
 
Resume AGEN2034 therapy per protocol.
 
Subjects with adrenal insufficiency may need to continue corticosteroids with mineralocorticoid component.
 

Suspicion of adrenal crisis (e.g., severe dehydration, hypotension, shock out of proportion to current illness)	
 
Delay or discontinue AGEN2034 therapy per protocol.
 
Rule out sepsis.
 
Stress dose of IV corticosteroids with mineralocorticoid activity.
 
IV fluids.
 
Consult endocrinologist.
 
If adrenal crisis ruled out, treat as above for symptomatic endocrinopathy.
 
	

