**Table 9: Renal Immune-related Adverse Event Management Algorithm**

Renal Immune-related Adverse Events		
Grade of Creatinine Elevation (NCI CTCAE v4.03)	Management	Follow-Up
Grade 1 Creatinine > upper limit of normal (ULN) and > than baseline but $\leq$ 1.5x baseline.	
 
Continue AGEN2034 therapy per protocol.
 
Monitor creatinine weekly
 
	
 
If returns to baseline: resume routine creatinine monitoring per protocol.
 
If worsens: treat as Grade 2 or Grade 3-4.
 

Grade 2-3 Creatinine > 1.5x baseline to $\leq$ 6x ULN.	
 
Delay AGEN2034 therapy per protocol.
 
Monitor creatinine every 2-3 days
 
0.5 to 1.0 mg/kg/day methylprednisolone IV or oral equivalent.
 
Consider renal biopsy
 
	
 
If returns to Grade 1: taper corticosteroids over at least 1 month, consider prophylactic antibiotics for opportunistic infections, and resume AGEN2034 therapy and routine creatinine monitoring per protocol.
 
If elevations persist <math>></math> 7 days or worsen: treat as Grade 4.
 

Grade 4 Creatinine > 6x ULN.	
 
Discontinue AGEN2034 therapy per protocol.
 
Monitor creatinine daily.
 
1.0 to 2.0 mg/kg/day methylprednisolone IV or IV equivalent.
 
Consult nephrologist.
 
Consider renal biopsy
 
	
 
If returns to Grade 1: taper corticosteroids over at least 1 month and add prophylactic antibiotics for opportunistic infections.
 

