## 7. ADVERSE EVENTS

### 7.1. Adverse Event Definitions

#### 7.1.1. Adverse Event

An AE is any untoward medical occurrence in a subject or clinical investigation subject administered a pharmaceutical product, which does not necessarily have a causal relationship with this treatment. An AE can therefore be any unfavorable and unintended sign (including an abnormal laboratory finding), symptom, or disease temporally associated with use of a medicinal product, whether or not considered related to the medicinal product. In cases of surgical or diagnostic procedures, the condition/illness leading to such a procedure is considered as the AE rather than the procedure itself.

The investigator is required to Grade the severity/intensity of each AE. Investigators will reference NCI CTCAE v4.03, which is a descriptive terminology that can be used for AE reporting. A general grading (severity/intensity) scale is provided at the beginning of the referenced document, and specific event Grades are also provided. If a particular AE's severity/intensity is not specifically Graded by the guidance document, the investigator is to revert to the general definitions of Grade 1 through Grade 5 and use his/her best medical judgement.

The 5 general Grades of AE severity are:

- Grade 1: Mild
- Grade 2: Moderate
- Grade 3: Severe
- Grade 4: Life-threatening or disabling
- Grade 5: Death related to AE

According to the Sponsor's convention, if a severity/intensity of Grade 4 or 5 is applied to an AE, the investigator must also report the event as an SAE as per [Section 7.2.2](#). However, a laboratory abnormality with a severity/intensity of Grade 4, such as anemia or neutropenia, is considered serious only if the condition meets one of the serious criteria described below.

In the case of death, the primary cause of death or the event leading to death should be recorded and reported as an SAE. "Fatal" will be recorded as the outcome of this respective event; death will not be recorded as separate event. Only if no cause of death can be reported (e.g., sudden death, unexplained death), might the death per se be reported as an SAE.

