### **7.1.2. Abnormal Laboratory Findings and Other Abnormal Investigational Findings**

Abnormal laboratory findings and other abnormal investigational findings (e.g., on an ECG trace) should not be reported as AEs unless they are associated with clinical signs and symptoms, lead to treatment discontinuation, or are considered otherwise medically important by the investigator. If an abnormality fulfills these criteria, the identified medical condition (e.g., anemia, increased ALT) must be reported as the AE rather than the abnormal value itself.

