#### **7.1.8. Predefined Potential AEs of Special Interest for Safety Monitoring**

Selected non-serious and SAEs defined below are considered AESIs and must be recorded as such on the Adverse Event case report forms/worksheets and reported within 24 hours to the Sponsor either by electronic media or paper. Sponsor Contact information can be found in the Investigator Trial File Binder (or equivalent).

Events of clinical interest for this trial include:

- Infusion-related reactions.
- An elevated AST or ALT lab value that is greater than or equal to 3X the upper limit of normal and an elevated total bilirubin lab value that is greater than or equal to 2X the upper limit of normal and, at the same time, an alkaline phosphatase lab value that is less than 2X the upper limit of normal, as determined by way of protocol-specified laboratory testing or unscheduled laboratory testing.

Note: These criteria are based upon available regulatory guidance documents. The purpose of the criteria is to specify a threshold of abnormal hepatic tests that may require an additional evaluation for an underlying etiology. The trial site guidance for assessment and follow up of these criteria can be found in [Section 5.6.4](#).

- Any AE that is reasonably suspected to be immune-mediated (ie, an irAE).

AESIs (both non-serious and serious AEs) identified in this guidance document from the date of first dose through 90 days following cessation of treatment, or 30 days after the initiation of a new anticancer therapy, whichever is earlier, need to be reported to the SPONSOR within 24 hours of the event, regardless of attribution to study treatment, consistent with standard SAE reporting guidelines and either by electronic media or paper.

Subjects should be assessed for possible AESIs prior to each dose. Lab results should be evaluated and subjects should be asked for signs and symptoms suggestive of an immune-related event. Subjects who develop an AE thought to be immune-related should have additional testing to rule out other etiologic causes. If lab results or symptoms indicate a possible irAE, then additional testing should be performed to rule out other etiologic causes. If no other cause is found, then it is assumed to be immune-related.

Any infusion reaction, regardless of Grade, must be reported in an expeditious manner and will be considered an AESI. The reporting of AESI is described in [Section 7.2.2](#).

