- **Thyroiditis:** autoimmune thyroiditis, thyroiditis, thyroid acute, thyroiditis chronic, thyroiditis fibrous chronic, thyroiditis subacute, immune-mediated thyroiditis

- **Neuroendocrine Disorders (Pituitary-Adrenal insufficiency):** Addison's disease, adrenal androgen deficiency, adrenal insufficiency, adrenal suppression, adrenocortical insufficiency acute, glucocorticoid deficiency, hypoaldosteronism, mineralocorticoid deficiency, hypophysitis, lymphocytic hypophysitis, hypopituitarism
- **Diabetes** without prior history: type 1 diabetes mellitus, diabetes mellitus, latent autoimmune diabetes in adults, diabetic ketoacidosis.
- **Nephritis:** autoimmune nephritis, lupus nephritis, nephritis, nephritis hemorrhagic, immune-mediated nephritis
- **Rash:** pemphigoid, rash, rash erythematous, rash generalized, rash macular, rash maculopapular, rash pruritic, rash papular, immune-mediated dermatitis
- **Pruritus:** pruritus, pruritus allergic, pruritus generalized

Other Immune-related AEs: myocarditis, immune-mediated myocarditis, uveitis, immune-mediated uveitis, iritis, vitiligo, psoriasis, myositis, immune-mediated myositis, rheumatoid arthritis, systemic inflammatory response syndrome, sarcoidosis, autoimmune disorder, meningitis, encephalitis, encephalitis autoimmune, immune-mediated encephalitis, encephalopathy, autoimmune encephalopathy, immune-mediated encephalopathy, Guillain-Barre syndrome, myasthenia gravis, demyelination, stomatitis, pancreatitis, autoimmune pancreatitis, pancreatitis acute, immune-mediated pancreatitis, immune-mediated gastritis, lichen planus, colitis ulcerative, Crohn's disease, inflammatory bowel disease, hemolytic anemia, immune-thrombocytopenia, immune thrombocytopenic purpura, aplastic anemia, bacytopenia, pancytopenia, immune-mediated pancytopenia

For each cluster, the analysis will summarize: the total incidence and number of all TEAEs included in the cluster and by severity grade, % of pts who received treatment with pituitary and hypothalamic hormones and analogues, with corticosteroids for systemic use, or with thyroid therapy (concomitant medications in, respectively, H01, H02 and H03 ATC2 groups indicated for AE and started following AE onset but no later than the date of AE resolution or 21 days from AE onset, whichever comes earlier), % leading to dose hold, % leading to drug discontinuation, % resolved, time to onset of first TEAE and duration of all TEAEs and TEAEs of grade ≥ 3 .

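### Protocol 7.1.2 does not make dose delay or corrective treatment a mandatory trigger for reporting a laboratory abnormality as an AE, so recording of asymptomatic hepatic and renal toxicity rests on investigator judgement

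*Protocol*

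**What the plan says.** Protocol 7.1.1 defines an AE broadly, as "any unfavorable and unintended sign (including an abnormal laboratory finding), symptom, or disease temporally associated with use of a medicinal product". Section 7.1.2 then narrows this for laboratory and other investigational findings: the default is not to report, "unless they are associated with clinical signs and symptoms, lead to treatment discontinuation, or are considered otherwise medically important by the investigator". When a finding does qualify, the medical condition is reported instead of the value.

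Other sections act on laboratory values without asking for symptoms:

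- Section 5.4.4.1 allows no dose reduction, so delay is the only modification short of stopping.
- Section 5.4.4.2.1, on liver tests: "If a subject has a baseline AST, ALT, or total bilirubin that is within normal limits, delay dosing for drug-related Grade" 2 or higher. The same section delays dosing for Grade 2 or higher creatinine.
- Table 7, for Grade 2 liver tests that persist beyond 5 to 7 days or worsen, gives methylprednisolone. It continues: "When LFT returns to Grade 1 or baseline, taper corticosteroids over at least 1 month", after which study drug may resume.
- Table 9, for Grade 2-3 creatinine, delays study drug and gives "0.5 to 1.0 mg/kg/day methylprednisolone IV or oral equivalent".

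Section 7.1.8 makes two relevant categories AESIs that must be recorded on the AE form. One is any AE reasonably suspected to be immune-mediated. The other is a purely laboratory hepatic criterion: AST or ALT at least 3 x ULN and bilirubin at least 2 x ULN, with alkaline phosphatase below 2 x ULN. On work-up, it begins: "If lab results or symptoms indicate a possible irAE", other causes are to be ruled out, and if none is found the event is assumed to be immune-related.

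**The concern.** Discontinuation obliges the site to open an AE record. A protocol-ordered hold, or a steroid course given for the same laboratory value, does not. The finding then becomes an AE only if the investigator calls it otherwise medically important. That phrase is close to the last seriousness criterion in 7.1.4, so a site could read it as a high bar that a Grade 2 ALT rise does not reach. With about 60 Phase 2 centers (Protocol 11.2), practice can differ.

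This matters because Section 7.2 attaches causality, duration, treatment given and action taken on study drug to the AE report. Frequency, severity and duration of TEAEs belong to a Phase 2 secondary endpoint (2.1.2) and a Phase 1 primary endpoint (2.1.1). The SAP's primary irAE analysis uses events as reported by investigators (7.6.2). A held and treated laboratory toxicity with no AE record drops out of all of these, and the omission can only lower the reported rates.

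**Working it through.** **1. Cases traced through 7.1.2.** Each subject is assumed to be symptom-free.

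| Case | What the protocol orders | Objective 7.1.2 trigger met? | Other route to the AE form |
|---|---|---|---|
| Grade 2 AST/ALT from normal baseline, drug-related | Delay (5.4.4.2.1); steroid if persistent or worse (Table 7); may resume | No | Judgement; 7.1.8 if suspected immune-mediated |
| Grade 2-3 creatinine, drug-related | Delay (5.4.4.2.1); steroid (Table 9); may resume on return to Grade 1 | No | Same |
| Laboratory-only hepatic AESI, not drug-related | 24-hour report regardless of attribution (7.1.8) | No | 7.1.8, which 7.1.2 does not mention |
| Same AESI, drug-related and above 3 x and 2 x ULN | Discontinue (4.4.1, Table 7) | Yes | Not needed |
| Asymptomatic TSH abnormality | Continue therapy (Table 8) | No | No hold or hormone is ordered, so the gap does not arise |

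The gap is real for the first two rows. For the third, two sections give different instructions.

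A related inconsistency affects the discontinuation trigger. Section 4.4.1 requires stopping for drug-related AST or ALT above 8 x ULN, while Table 7 says to discontinue above 5 x ULN. Between 5 and 8 x ULN, whether the trigger is met depends on which text the site follows. The two must be reconciled; no view is taken here on which is right.

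**2. What is kept without an AE record.** Protocol 8.3.4.2 summarizes worst CTCAE grades and shifts. SAP 7.6.4 grades ALT, AST, bilirubin and creatinine and adds an eDISH plot. SAP 7.6.2 adds worsening from baseline and liver-test elevations of at least 2 x ULN. All come from laboratory data. What is lost is causality, action taken, treatment, duration as an event, and the irAE classification.

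**3. The SAP clusters.** For each cluster SAP 7.6.2 reports the percentages "leading to dose hold, % leading to drug discontinuation, % resolved", together with the percentage given systemic steroids, thyroid therapy or pituitary hormones. Membership is by listed Preferred Term. The hepatitis list has no ALT-, AST- or bilirubin-increased term, and the nephritis list has no creatinine-increased term. An AE recorded as increased ALT, which is 7.1.2's own example, would stay outside the cluster even after the fix. An event enters only if the site names a listed condition, such as hepatotoxicity or immune-mediated hepatitis.

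**4. Arithmetic.** The only design figure tied to AE capture is the probability, stated as at least 77%, of observing an AE with a 1% rate in 150 subjects (Protocol 8.1.2). It reproduces: 1 - 0.99^150 = 0.7785.

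That figure treats every case as recorded. If a fraction f reaches the AE form, it becomes 1 - (1 - 0.01f)^150:

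| f (assumed) | Probability of at least one recorded AE |
|---|---|
| 1.00 | 77.9% |
| 0.90 | 74.2% |
| 0.75 | 67.7% |
| 0.50 | 52.9% |
| 0.25 | 31.3% |

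The documents give no value of f and no rate of asymptomatic hepatic or renal toxicity. The table shows sensitivity only. It applies only to an event whose cases all fall under the discretionary rule.

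**The case against.** The strongest reply is that 7.1.2 already covers these events. An investigator who holds drug and starts methylprednisolone can hardly call the finding unimportant. Tables 7 and 9 are irAE algorithms, applied after non-inflammatory causes are ruled out (5.6.4, 5.6.6). A subject treated under them is being managed for an irAE, and Sections 5.6 and 7.1.8 require irAEs to be reported. Section 7.2 also says unfavorable changes in condition are recorded as AEs, and it refers to eCRF completion conventions that are not among the documents.

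Much of this stands. It rules out reading 7.1.2 as excluding such events, and it makes the steroid-treated cases less likely to be missed than those only held. It does not close the gap. The judgement trigger works against a default of not reporting. The irAE category in 7.1.8 is framed as an AE suspected to be immune-mediated, so 7.1.2 still bears on whether the finding counts as an AE. A reader can take 7.1.8 as a specific rule that overrides the general one, but neither section says so.

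Two wider readings are tempting and fail. A reader might add thyroid toxicity. Table 8's row for "Asymptomatic thyroid-stimulating hormone (TSH) abnormality" continues therapy and orders no delay, steroid or hormone; hormone treatment sits in the symptomatic row, which the first 7.1.2 trigger covers. (TSH and T4 are not in the SAP's graded laboratory list, but that is a separate matter.) A reader might also infer that the clusters' dose-hold and treatment percentages are understated; the term lists largely prevent that.

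**Conclusion.** The point holds as a gap in a reporting rule, worth a cheap correction. Followed as written, 7.1.2 leaves AE-side information on protocol-ordered holds and corrective treatment for asymptomatic hepatic and creatinine abnormalities to investigator judgement. It also makes no exception for the laboratory-only hepatic AESI. Recording may therefore be incomplete and may differ between sites, in the TEAE and investigator-reported irAE tables.

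A reader might go further and conclude that this toxicity is under-recorded, or that the safety endpoint is biased by a given amount. The documents do not support either. Reporting is permitted in every case, the endpoint is TEAEs and laboratory abnormalities together, and the laboratory half is analysed whether or not an AE form exists. Any percentage shortfall would rest on an event rate and an unreported fraction that the documents do not supply. The conclusion assumes that the unseen eCRF conventions do not already add the missing triggers.

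**What to change.** In Protocol 7.1.2, extend the list of triggers so that a laboratory abnormality is also an AE when it leads to a dose delay or interruption, requires corrective treatment, or meets an AESI definition in 7.1.8. Keep the rule that the medical condition is reported instead of the value. Align the wording with 7.1.1, and check that the eCRF completion conventions say the same.

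The change is one sentence in the next amendment plus the matching convention. It alters AE reporting only and leaves every dosing, delay and treatment rule as it stands. The cost is more AE entries and slightly higher reported AE rates. If the amendment comes after many subjects are enrolled, the study report should note the date, since events before and after it are recorded under different rules.

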### **7.1.3. Adverse Drug Reaction**

An ADR is defined in this trial as any AEs suspected to be related to AGEN2034 by the investigator and/or Sponsor.

### **7.1.4. Serious Adverse Event**

An SAE is any untoward medical occurrence that at any dose:

- Results in death.
- Is life-threatening.

**Note:** The term “life-threatening” in this definition refers to an event in which the subject is at risk of death at the time of the event; it does not refer to an event that hypothetically might cause death if it were more severe.

- Requires in-patient hospitalization or prolongation of existing hospitalization
- Results in persistent or significant disability/incapacity
- Is a congenital anomaly/birth defect
- An overdose of Sponsor's product, as defined in [Section 7.5](#)
- Is otherwise considered as medically important

Important medical events that may not result in death, be life-threatening, or require hospitalization may be considered as SAEs when, based on appropriate medical judgement, they may jeopardize the subject or may require medical or surgical intervention to prevent one of the outcomes listed in this definition. Examples of such events include allergic bronchospasm requiring intensive treatment in an emergency room or at home, blood dyscrasias or convulsions that do not result in subject hospitalization, or development of drug dependency or drug abuse.

For purposes of reporting, any suspected transmission of an infectious agent via a study drug is also considered a serious adverse reaction, and all such cases should be reported in an expedited manner as described in [Section 7.2.2](#).

